#### **4.6.2. Benefit Assessment**

In the absence of radical cure treatment, a percentage of subjects with *P. vivax* malaria will relapse due to the liver being infected with hypnozoites (the dormant form of the parasite). *P. vivax* can cause a debilitating fever as it preferentially invades reticulocytes as well as causing bystander hemolysis, which can also lead to the development of anemia. Repeated relapses are similarly debilitating and may result in further episodes of fever, weight loss, malnutrition and high output heart failure. Other consequences are loss of work, time at school missed and hospitalization due to vomiting, dehydration and anemia (resulting in the need for transfusion).

Subjects may benefit from participating in this study since they will be closely followed for 6 months, thus ensuring that any malaria recurrences will be appropriately treated and concurrent conditions managed. Any subject who has not relapsed by the 6 month timepoint will be treated with open label PQ for 14 days, to ensure that all participants receive anti-hypnozoite medication as part of the study. In the future, patients with *P. vivax* malaria may benefit from TQ since it can be administered as a single oral dose (due to its long half life) and is therefore a more convenient treatment regimen compared with the standard 14 day regimen of PQ, with the potential to improve patient compliance. Improved compliance should lead to improved clinical outcomes for patients with *P. vivax* malaria by further reducing relapse rates.

#### **4.6.3. Overall Benefit:Risk Conclusion**

TQ is being developed with the aim of a benefit:risk profile which is at least as good as the current standard therapy PQ. It is anticipated that this study will demonstrate that a convenient single dose of TQ is effective and safe when given in conjunction with an ACT for radical cure of *P. vivax* malaria and has a comparable profile to a 14 day regimen of PQ (15mg). All subjects will be closely observed and any adverse effects associated with study treatment or relapses of malaria will be promptly managed to minimize any risk to subjects participating in the study. G6PD deficient subjects will be excluded to avoid hemolytic risks associated with hypnozoite treatment.

## 5. SELECTION OF STUDY POPULATION AND WITHDRAWAL CRITERIA

Specific information regarding warnings, precautions, contraindications, adverse events, and other pertinent information on the GSK investigational product or other study treatment that may impact subject eligibility is provided in the TQ Investigator Brochure.

Deviations from inclusion and exclusion criteria are not allowed because they can potentially jeopardize the scientific integrity of the study, regulatory acceptability or subject safety. Therefore, adherence to the criteria as specified in the protocol is essential.

### 5.1. Inclusion Criteria

A subject will be eligible for inclusion in this study only if all of the following criteria apply:

AGE and SEX
1. Male subjects $\geq 18$ years at the time of signing the informed consent.

TYPE OF SUBJECT AND DIAGNOSIS INCLUDING DISEASE SEVERITY
2. The subject has a positive Giemsa smear for P. vivax (mixed infection with P. falciparum is acceptable).
3. The subject has a parasite density of $>20$ / $\mu$ L.
4. Glucose-6-phosphate dehydrogenase (G6PD) normal using a suitable qualitative assessment e.g. NADPH qualitative fluorescent spot test (Trinity Biologicals, USA).
5. The subject has a QTcF of $<450$ msec.  N.B. Reading based on an average of triplicate ECGs obtained over a brief recording period by machine.
6. The subject is willing and able to comply with the study protocol.

INFORMED CONSENT
7. Capable of giving signed informed consent as described in Section 7.2 which includes compliance with the requirements and restrictions listed in the consent form and in this protocol.

## 5.2. Exclusion Criteria

A subject will not be eligible for inclusion in this study if any of the following criteria apply:

### CONCURRENT CONDITIONS/MEDICAL HISTORY (INCLUDES LIVER FUNCTION AND QTc INTERVAL)

1. Severe *P. vivax* malaria as defined by WHO criteria (see Section [12.4 Appendix 4](#)).
2. Severe vomiting (no food or inability to take food during the previous 8 hours).
3. Screening hemoglobin (Hb) concentration <8g/dL.
4. Liver function test ALT >2 x ULN.
5. Any clinically significant concurrent illness (e.g., pneumonia, septicemia), significant pre-existing conditions (e.g., renal disease, malignancy, Type 1 diabetes), conditions that may affect absorption of study treatment (e.g., vomiting, severe diarrhea), or clinical signs and symptoms of severe cardiovascular disease (e.g., uncontrolled congestive heart failure, severe coronary artery disease). These abnormalities may be identified on the screening history and physical or laboratory examination.
6. History of hypersensitivity, allergy or adverse reactions to DHA or other artemisinins, piperazine, tafenoquine or primaquine.

### CONCOMITANT MEDICATIONS

7. Subject has previously received treatment with tafenoquine, or has received treatment with any other investigational drug within 30 days of study entry or within 5 half-lives, whichever is longer.
8. Subject has taken anti-malarials (e.g., ACTs, mefloquine, primaquine, quinacrine) or drugs with anti-malarial activity within the past 30 days (see Section [12.5 Appendix 5](#)).
9. Subjects who will likely require the use of medications from the prohibited medications list or have taken them in the past 30 days (see Section [12.5 Appendix 5](#)) which include the following medications and medication classes:
  - Drugs with hemolytic potential
  - Drugs known to prolong the QTc interval including:
    - Antiarrhythmics (e.g. amiodarone, disopyramide, dofetilide, ibutilide, procainamide, quinidine, hydroquinidine, sotalol).
    - Neuroleptics (e.g. phenothiazines, sertindole, sultopride, chlorpromazine, haloperidol, mesoridazine, pimozide, or thioridazine) and antidepressive

### CONCOMITANT MEDICATIONS

agents.

- Certain antimicrobial agents, including agents of the following classes: macrolides (e.g. erythromycin, clarithromycin), fluoroquinolones (e.g. moxifloxacin, sparfloxacin), imidazole and triazole antifungal agents and also pentamidine and saquinavir.
- Certain non-sedating antihistamines (e.g. terfenadine, astemizole, mizolastine).
- Cisapride, droperidol, domperidone, bepridil, diphemanil, probutol, levomethadyl, methadone, vinca alkaloids, arsenic trioxide.
- The biguanides: phenformin and buformin (but excluding metformin-see Section 6.9.2).
- Drugs that are substrates of the renal transporters OCT2, MATE1 and MATE2 and have a narrow therapeutic index (for example, the antiarrhythmic agents: dofetilide, procainamide and pilsicainide).

### RELEVANT HABITS

10. Anticipated to be unable to consume daily study treatment under direct supervision by the research team.
11. Previous participation in the present clinical trial, i.e., subjects experiencing relapse during or after the study period may not be enrolled as a new subject.
12. History of illicit drug abuse or heavy alcohol intake, such that full participation in the study could be compromised.

### CONTRAINDICATIONS

13. Any contraindication in the opinion of the Investigator to DHA-PQP or primaquine administration (refer to locally approved prescribing information for primaquine) such as:
  - Family history of sudden unexplained death (DHA-PQP)
  - Known congenital QTc prolongation (DHA-PQP)
  - Known history of a medical condition known to prolong the QT interval: e.g. myxoedema, cardiomyopathies, recent myocardial infarction (DHA-PQP)
  - History of symptomatic cardiac arrhythmias or with clinically relevant

bradycardia (DHA-PQP)

- Cardiac illnesses predisposing to arrhythmias e.g. severe hypertension, left ventricular hypertrophy, cardiomyopathies, cardiac failure with reduced ejection fraction (DHA-PQP)
- Presence of an electrolyte disturbance particularly hypokalemia, hypocalcemia, hypomagnesemia (DHA-PQP)
- Rheumatoid arthritis, lupus erythematosus and other systemic conditions that may cause granulocytopenia (primaquine)
- History of hemolytic anemia, methemoglobinemia and leucopenia (primaquine)

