##### Justification of DHA-PQP dose regimen:

The DHA-PQP dose regimen will be in accordance with the approved European prescribing information for Eurartesim (Eurartesim SmPC). Headache, anaemia, QTc prolongation, tachycardia, asthenia and pyrexia are the most common adverse events associated with this regimen in adults. Clinical trial data showed that QTc prolongation occurred more frequently and to a larger extent following Eurartesim than with comparators. In a Phase III study, before the third dose of Eurartesim, 3/767 patients (0.4%) had a QTcF value of >500ms versus none in the comparator group (Eurartesim SmPC). Modest QTc prolongation was also detected on Day 2 following dosing with DHA-PQP plus PQ in a recent Indonesian soldier study; the effect returned to baseline by Day 7 (Nelwan, 2015). No clinically significant drug-drug interaction was observed between DHA-PQP and TQ in GSK Study 200951. However, given the piperazine-

induced QTc elongation observed, ECGs will be monitored in line with the Eurartesim prescribing information.

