QTcF prolongation	
The product labelling for DHA-PQP (Eurartesim SmPC) notes that in clinical trials, QTc prolongation occurred more frequently and to a larger extent following DHA-PQP than with comparators. Before the 3rd dose, in one of two Phase III studies, 3/767 (0.4%) subjects were reported to have a QTc value >500msec versus none in the comparator group. Absorption of piperazine is increased in the presence of fatty food which may increase its effect on QTc interval.
 
Preclinical studies determined that tafenoquine has a low potential for QTc prolongation. A tafenoquine thorough QT study did not show elongation of the QTcF at clinical doses. In the 200951 DDI study, the greatest increase in QTc was observed 4 hours after the last dose of DHA-PQP in both the DHA-PQP+TQ group and the DHA-PQP alone group; this time point will be a key point of interest for ECGs in this study.
 
The label for primaquine (US prescribing information) notes that primaquine has the potential for QT interval prolongation and advises the need for ECG monitoring in subjects with relevant underlying comorbid conditions, as well as during concomitant administration with QT interval prolonging agents.
	
 
• ECG monitoring will be conducted in this study appropriate to DHA-PQP and primaquine labels. Study treatment stopping criteria are provided for QTc prolongation.
 
• DHA-PQP will be dosed without food.
 

Potential Key Risks of Clinical Significance	Summary of Data/Rationale for Risk	Mitigation Strategy
Study Design		
Risk of relapse in DHA-PQP alone arm	Subjects in the DHA-PQP alone arm are at increased risk of relapse during the study compared to subjects randomized to DHA-PQP+primaquine or DHA-PQP+tafenoquine	
 
• Subjects will be under close observation throughout the study and will receive standard of care treatment at first sign of recurrent malaria (symptomatic or asymptomatic). On site clinic facilities will be available 24 hours a day, 7 days a week to ensure prompt management of any subject who develops recurrent malaria.
 
• At the end of the study, any subject who has not relapsed will be given open label PQ 0.5mg/kg daily for 14 days to minimize the likelihood of relapses after the study.
 

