### 6.1. Treatment Assignment

Subjects will be assigned to one of three blinded treatment arms: DHA-PQP alone, DHA-PQP plus TQ or DHA-PQP plus PQ in accordance with the randomization schedule generated by Clinical Statistics, prior to the start of the study, using validated internal software.

Subjects will be randomized via an interactive web recognition system (IWRS) to blinded study treatment after beginning administration of open label DHA-PQP. Each subject scheduled to receive blinded study treatment will receive a treatment allocation number (i.e. randomization number) via the IWRS system on Day 1. The treatment allocation

ratio will be 1:1:1. Once a randomization number has been allocated to a subject, it cannot be re-assigned to any other subject.

Open label DHA-PQP will be administered daily over three consecutive days. Each dose will be taken at least 3 hours after the last food intake and no food will be taken for 3 hours after each dose. If a subject vomits within 30 minutes of taking DHA-PQP on Days 1 to 3, the whole dose should be re-administered; if the subject vomits within 30-60 minutes, half the dose should be re-administered. Repeat dosing with DHA-PQP should not be attempted more than once. If the repeat dose is vomited on Day 1, the subject should be withdrawn from the study and given appropriate rescue medication as outlined in Section 6.9.1.2.

Blinded study treatment will be administered daily over 14 days together with food (at least 3 hours after dosing with DHA-PQP on Days 1, 2 and 3). If the subject vomits within 1 hour following dosing, a repeat dose should be given. If the repeat dose is vomited on Day 1, the subject should be withdrawn from the study and given appropriate rescue medication as outlined in Section 6.9.1.2.

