- Methemoglobin levels will be assessed using a non-invasive machine. This assessment will be performed by an independent person who will not participate in any other study procedures at the site. The data will be transmitted securely to GSK data management and will not be shared with other site staff unless result is above a preset threshold that requires a safety assessment (refer to SRM).
- A12 lead ECG will be performed with the subject in a semi-supine position having rested in this position for at least 10 minutes beforehand. Measurements that deviate substantially from previous readings will be repeated immediately. Three (3) measurements will be taken at screening, five minutes apart.
  - The mean heart rate, RR interval, QRS duration, uncorrected QT interval and QTcF (QT corrected by Friderica's formula) will be calculated from automated ECG readings and abnormal findings will be recorded in the eCRF. The mean value recorded pre-DHA-PQP will be classified as baseline.
- A blood sample will be collected for CYP2D6 genotyping and possible G6PD genotyping. The extracted nucleic acid sample for G6PD genotyping will be stored and may be analyzed in the event of an SAE due to hemoglobin decline where a repeat G6PD phenotype assay would not define G6PD status (e.g. transfusion given or high reticulocyte count).
- Subjects who have undergone screening and meet the label requirements for DHA-PQP dosing can receive open label DHA-PQP if the clinician deems that appropriate (e.g. symptomatic disease), and at least 3 hours have elapsed since last food intake. Thus, DHA-PQP may be commenced whilst the results of the hematology, clinical chemistry or G6PD deficiency screening tests are pending. Once these laboratory test results are available and the subject eligibility is confirmed, they will be randomized via the IWRS to blinded study treatment. The first dose of blinded study treatment will be administered with food at least 3 hours after DHA-PQP on Day 1 or Day 2.

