## 7.5.5 Clinical Safety Laboratory Assessments

Clinical chemistry and hematology samples will be analyzed by the local laboratory. All protocol required laboratory assessments, as defined in [Table 1](#) and [Table 2](#), must be conducted in accordance with SRM and at the timepoints indicated in the Protocol Time and Events Schedule (Section [7.1](#)).

All laboratory data will be used for the purpose of safety analysis and reporting for this study. Any laboratory tests the attending physician or investigator deems necessary for the care and safety monitoring of the study subjects will be conducted by the local laboratory. All laboratory results that are considered clinically significant should be recorded as AEs.

Hemoglobin and/or hematocrit measurements that deviate substantially from previous readings should be immediately repeated via venous sampling. If a protocol-defined Hb drop is observed upon repeat testing (Section [7.5.1.1](#)), all additional clinical chemistry labs should be obtained immediately.

If, after Day 3, platelet counts are  $<5 \times 10^4$  per  $\mu\text{L}$ , the test should be repeated or confirmed with a manual slide reading.

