**Table 2 Clinical Chemistry Tests**

Creatinine	BUN	Total bilirubin	Indirect bilirubin
AST	ALT	ALP	CPK

Urinalysis will be conducted at screening. Urine (approximately 20mL mid-stream urine) will be analyzed for protein, glucose, ketones, bilirubin, blood, nitrites and urobilinogen by dipstick method. Sediment microscopy will be performed if the leukocyte, nitrites, protein, or occult blood is abnormal and will include analysis for white blood cells, red blood cells, hyaline casts, granular casts and cellular casts.

Methemoglobin status will be assessed daily up to Day 14, on alternate days up to Day 28 and on Day 60 (or at relapse/withdrawal from study) (See Section [7.1](#)). Subjects with anemia may have symptomatic methemoglobinemia at levels lower than subjects with normal hemoglobin levels (symptoms typically do NOT occur with metHb values  $<20\%$  in subjects with normal hemoglobin levels).

All laboratory tests with values that are considered clinically significantly abnormal during participation in the study should be reported as AEs and then tests repeated until the values return to normal or baseline. If such values do not return to normal within a period judged reasonable by the investigator, the etiology should be identified and the sponsor notified.

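### Criterion 13 lists a current electrolyte disturbance as a DHA-PQP contraindication, but no protocol-required test measures potassium, calcium or magnesium

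*Protocol*

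**What the plan says.** Criterion 13 in Section 5.2 excludes men with a contraindication to DHA-PQP or primaquine in the investigator's opinion and gives examples. One is "Presence of an electrolyte disturbance particularly hypokalemia, hypocalcemia, hypomagnesemia (DHA-PQP". No threshold and no test is attached to it.

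Section 7.2(a) calls for hematology and clinical chemistry before DHA-PQP and refers to Section 7.5.5. That section defines the required tests by Table 1 (hematology) and by "Table 2 Clinical Chemistry Tests". Beyond these it allows for "Any laboratory tests the attending physician or investigator deems necessary for the care and safety monitoring of the study subjects", run at the local laboratory.

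On timing, Section 7.2(a) lets a screened man start DHA-PQP if the clinician thinks it appropriate and he is found to "meet the label requirements for DHA-PQP dosing". It adds: "Thus, DHA-PQP may be commenced whilst the results of the hematology, clinical chemistry or G6PD deficiency screening tests are pending". Section 4.1 requires all laboratory evaluations to be available, and eligibility confirmed, before randomisation. Section 6.1 says: "Subjects will be randomized via an interactive web recognition system (IWRS) to blinded study treatment after beginning administration of open label DHA-PQP". The Time and Events table places the inclusion and exclusion check in the Day 1 column before DHA-PQP.

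**The concern.** Several other examples in criterion 13 are worded as known conditions or as history, and an interview can settle those. This one is a present biochemical state. A man can have a low potassium, calcium or magnesium without symptoms that would lead anyone to test for it, so applying the bullet reliably needs a measurement.

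What is at stake is participant safety. DHA-PQP prolongs QTc, and a man with an unsuspected disturbance could receive a drug that the protocol itself lists as contraindicated for him, with every required step followed. The laboratory review before randomisation does not close the gap, because the chemistry reviewed there does not contain the three electrolytes that criterion 13 names.

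**Working it through.** The plan gives no figure on this point, so the check compares the criterion with every laboratory list in the two documents and then counts doses.

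**Which required tests measure potassium, calcium or magnesium?**

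| Source | Content | K, Ca or Mg |
|---|---|---|
| Protocol Table 1 | hemoglobin, hematocrit, platelets, MCV, WBC, RBC, WBC differential (7 items) | 0 of 7 |
| Protocol Table 2 | creatinine, BUN, total bilirubin, indirect bilirubin, AST, ALT, ALP, CPK (8 items) | 0 of 8 |
| Screening urinalysis, Section 7.5.5 | dipstick, with microscopy if abnormal | none |
| Work-up after a hemoglobin drop, Section 5.4.2 | blood counts, reticulocytes, the Table 2 analytes, LDH, urine inspection and dipstick | none |
| Liver event follow-up, Appendix 2 | liver, viral and related tests | none |
| SAP Section 11.8.1 concern ranges, chemistry | 8 analytes, the same as Table 2 | none |

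For Tables 1 and 2 together: 7 + 8 = 15 items, of which 0 measure a named electrolyte. The SAP chemistry list matches Table 2 analyte for analyte, so it is unlikely that a row was lost when the protocol table was read from PDF. The severe-malaria definition in Appendix 4 (exclusion criterion 1) also mentions electrolyte disturbance, again with no test attached.

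**How many DHA-PQP doses can precede the laboratory results?** DHA-PQP is given once daily on Days 1 to 3, so there are 3 doses.

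- Lower end: an early start is allowed, not required. A clinician may wait for chemistry, and then 0 of 3 doses precede the results.
- Upper end: under Section 4.1 the first blinded dose may fall on Day 2, at least 3 hours after DHA-PQP. If results arrive only after that day's DHA-PQP, the Day 1 and Day 2 doses have both been given: 1 + 1 = 2 of 3.

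The range is 0 to 2. The upper end rests on Section 4.1, which allows for a Day 2 start. Section 6.1 and the Time and Events table place the IWRS call on Day 1. Read strictly, they would require results on Day 1, and the upper end would be 1.

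**How often would this happen?** The documents give no frequency of unsuspected electrolyte disturbance in this population. None is assumed here, so the number of men affected cannot be estimated.

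**The case against.** The strongest reply is that criterion 13 is a matter of judgement by design. Other examples in the same list, such as cardiomyopathy or lupus, have no dedicated confirmatory test either, and Section 7.5.5 lets the investigator order whatever is needed. The label condition must be met before DHA-PQP is given, and the label or the Study Reference Manual may require electrolytes. This stands in part: the plan does not contradict itself, and a check outside these documents cannot be ruled out. But a discretionary test is ordered when something is suspected, and the gap concerns the man in whom nothing is.

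The second reply is that the risk behind the bullet is controlled by other means. Entry requires an averaged triplicate QTcF below 450 msec. Severe vomiting, severe diarrhea, renal disease and QT-prolonging drugs are excluded. Two ECGs are scheduled on Day 3, the later one timed to the interaction study's finding that "the greatest increase in QTc was observed 4 hours after the last dose of DHA-PQP". Treatment stops at QTcF above 500 msec. This stands and is why the point is minor. None of these controls measures an electrolyte, though, and the protocol lists electrolyte disturbance in addition to its ECG criterion, not in place of it.

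A reader might infer from Section 6.1 that at least one dose always precedes the laboratory results. The text does not support that. It fixes when randomisation happens, not when results arrive. An early start is optional, and eligibility is to be checked before the first DHA-PQP dose.

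**Conclusion.** The gap is real and small. No protocol-required test (0 of 15 items in Tables 1 and 2, and none in any other panel) measures the three electrolytes named in criterion 13. Detecting an unsuspected disturbance depends on a discretionary test or on a requirement in a document not seen here. Between 0 and 2 of the 3 DHA-PQP doses can come before laboratory results.

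Two stronger readings should be resisted. One is that contraindicated men were in fact dosed: the documents give no electrolyte values and no prevalence, and investigators may have tested at their discretion. The other is that efficacy is compromised: DHA-PQP is given open label to all three arms before or at randomisation, and nothing here touches the primary comparison or its analysis.

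The conclusion assumes that Tables 1 and 2 are complete as reproduced, which the SAP list supports for chemistry, and that neither the label nor the Study Reference Manual adds a mandatory electrolyte test.

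**What to change.** For any further use of this protocol, add potassium, calcium and magnesium to Table 2 for the Day 1 chemistry sample that is already drawn before DHA-PQP. State in Section 7.2 that the investigator reviews them with the other screening chemistry, before the first dose where results are available promptly. Do not make treatment of acute malaria wait for them: how far to delay a dose is a clinical trade-off. A man found abnormal after DHA-PQP has started, and so not randomised, is already classed as a Screen Failure under Section 5.3.

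The cost is a short amendment, a small laboratory charge and possibly a few screen failures. This assumes that the local laboratory can run the three tests, which the documents do not state.

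SAP Section 2.1 records that 150 participants had been randomised, so an amendment cannot help them. For those men the study report should state that the electrolyte bullet of criterion 13 was not verified by a protocol-required test. That costs one sentence.
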